7.2.2. Study Day

The day of first dose of treatment administration is defined as study Day 1. Subsequent days are numbered consecutively (Day 2, Day 3, etc.). Prior to the day of first dose of treatment administration, study days are numbered sequentially with negative values (i.e., Day -1, Day -2, etc.). There is no Day 0.

7.2.3. End of Study (EOS)

The EOS ("study completion") is defined as the date of the last Protocol-specified visit/assessment (including telephone contact) for the last subject in the study. Subjects attending the EOS who require further follow-up may be entered into a separate long-term follow-up study.

7.3. Missing Data

In general, missing endpoint data will not be imputed. All analyses will be based on observed endpoints and related data. Sections 7.3.1 and 7.3.2 note the situations where missing data will be imputed.

This document is confidential.

7.3.1. Handling of Missing Dates/Months/Years for Prior/Concomitant Therapies

If the medication cannot be classified into concomitant or prior status due to incomplete start and/or stop date, the rules below will be applied for the classification.

For start date,

- If the year and month are observed but the day is missing, the first day of the month will be used unless month and year are the same as month and year of first dose date then impute using the day of first dose date.
- If the year is observed but the month and day are missing, the first day of the year, 01 Jan, will be used unless year is the same as first dose date then the first dose date will be used.
- If the start date is completely missing, the medication will be considered concomitant unless the stop date is before treatment administration.
- If the start and stop dates are both completely missing, a therapy will be considered concomitant.

For end date,

- If the year and month are observed but the day is missing, the last day of the month will be used unless month and year are the same as month and year of last dose date, then impute the last dose date.
- If the year is observed but the month and day are missing, the last day of the year, 31 Dec, will be used unless year is the same as last dose date then the last dose date will be used.
- If the end date is completely missing, if medication is still ongoing, then missing end date is not supposed to be imputed. If the medication is not ongoing and the start date is prior to first dose date, the end date will be imputed using 1st dose date.
- If both start and end dates are completely missing, medication will be considered concomitant.

The original partial or missing date will be shown in listings for all prior and concomitant medications.

7.3.2. Adverse Events Dates

For AEs with incomplete dates, the following rules will be used to impute start and/or stop dates for the sole purpose of determining if an AE is treatment emergent. Imputed dates will not appear in the data listings.

For partial start dates:

- If the month and year of AE onset are provided but day is missing
 - If the month and year match the month and the year of the date of first dosing administration, then the date of first dosing administration will be used and the AE will be considered treatment emergent.
 - Otherwise, the first day of the month will be used.
- If the year of AE onset is provided, but the month and day are missing
 - If the year matches the year of the first dosing administration, then the date of first dosing administration will be used.
 - Otherwise, 01 Jan will be used.
 - If the stop date is not missing and the imputed onset date is after the stop date, then the stop date will be used.
 - If the onset date is completely missing and the stop date is on or after the date of first dose, the event will be considered a treatment emergent adverse event (TEAE).

This document is confidential.

If both onset date and stop date are missing, the event will be considered a TEAE. Partial stop dates will not be imputed in this instance.

7.4. Visit Windows

There will be no derivation for visit windows in terms of summary assessments. Nominal visits will be used for by-visit tables.

For data with repeated observations at a given visit (e.g., laboratory assessments), the earliest of the available non-missing values at a visit should be used in summary tables. Other observations will be considered as unscheduled visits. For the purpose of tabulations, the unscheduled post-baseline values generally will be excluded from summary tables but will be included in the listing. Unscheduled visits will be considered for analyses of worst Common Terminology Criteria for Adverse Events (CTCAE) laboratory grades.

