- o. The subject will receive study drug doses for home administration on Visit 1/Day 1 for treatment Days 2 through 4 and on Visit 2/Day 5 for treatment Days 5 (second dose) through 9 and on Visit 3/Day 10 for treatment Day 10 (second dose).
- p. The first 2 subjects in Cohorts A and B will consist of 1 active and 1 placebo subject. Both subjects will be observed for at least 2 days after dosing and if there are no Grade 2 or greater AEs assessed as treatment-related, dosing for the remaining subjects will proceed. Study drug will be administered as 1 fractionated dose of AP-PA02 or placebo (1 dose distributed over 2 administrations given 6 hours apart on the same day on Day 1 and 10-12 hours apart each day on the remaining days) for 10 consecutive days. Subjects will administer AP-PA02 or placebo at home on days they do not visit the clinic. AP-PA02 and placebo will be administered in the clinic during Visit 1/Day 1 (both doses), Visit 2/Day 5 (morning dose only), and Visit 3/Day 10 (morning dose only).
- q. The subject's current antipseudomonal inhaled antibiotic will be administered at Baseline, and for a total of 28 days, 10 days of study treatment and the following 18 days, for subjects in Cohort B only.
- r. Only SAEs will be recorded from Screening until the first dose of AP-PA02 or placebo. After the first dose of AP-PA02 or placebo all AEs will be recorded.

AE = adverse event; CFU = colony-forming units; CT = computerized tomography; d = days; ECG = electrocardiogram; EOS = End of Study; ET = Early Termination; FEF₂₅₋₇₅ = forced expiratory flow between 25% and 75% of the forced vital capacity; FEV₁ = forced expiratory volume; FVC = forced vital capacity; GLI = Global Lung Initiative; HBsAg = hepatitis B surface antigen; HCV = hepatitis C virus; HIV = human immunodeficiency virus; HRCT = high-resolution computerized tomography; LCQ = Leicester Cough Questionnaire; QOL-B = Quality of Life-Bronchiectasis; RNA = ribonucleic acid; SAE = serious adverse event; SpO₂ = oxygen saturation; U = Unscheduled.

Table 2. Timing of Sample Collection and Procedures for the Treatment Period

Visit	Treatment Period								
	1			2		3			
Day	1			5		10			
Time	Prior to first dose	30 minutes after first dose	1 hour after first dose	1 hour after second dose	Prior to first dose	30 minutes after first dose	Prior to first dose	30 minutes after first dose	1 hour after first dose
Induced sputum sample (required)				*	*				*
Sputum culture					X				X

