11.5. Vital Signs

Vital sign measurements will consist of blood pressure (systolic and diastolic), oxygen saturation, heart rate, respiratory rate, and body temperature. Descriptive summaries (number of subjects, mean, standard deviation, median, minimum, and maximum) of actual values and changes from baseline will be presented for each visit and time point. These summaries will be presented for the safety population and by treatment group. Vital signs will be performed at all study visits at prespecified time points per the Timing of Sample Collection and Procedures for the Treatment Period in Table 2 of the Protocol Appendix A.

Temperature will be summarized in Celsius (C) units. Fahrenheit (F) will be converted to Celsius using the following conversion:

$$\text{Temperature (in } ^\circ\text{C)} = 5/9 \text{ (Temperature [in } ^\circ\text{F]} - 32)$$

Potentially clinically significant (PCS) vital sign abnormalities will be categorized based on Table 13.3.1 and summarized by treatment group and assessment visit.

Table 13.3.1 Potentially Clinically Significant Values for Vital Signs

Vital Sign Parameter	Units	Criteria for PCS Values (Observed values)		Criteria for PCS values (Change from Baseline values)	
		High	Low	Increase	Decrease
Heart rate (sitting)	Beats/min	>120	<40	NA	NA
Systolic Blood Pressure (sitting)	mmHg	>180	<90	≥30	≥30
Diastolic Blood pressure (sitting)	mmHg	>110	<50	≥20	≥20
Oxygen Saturation (sitting)	%	NA	<92	≥5	≥5

A by-subject line plot will be provided by treatment group. Vital sign data will be listed chronologically by subject and visit for each vital sign parameter.

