11.6. Twelve-Lead Electrocardiograms

A 12-lead ECG will be performed locally at the site according to the Schedule of Assessments in Table 1 of the Protocol Appendix A and Timing of Sample Collection and Procedures for the Treatment Period in Table 2 of the Protocol Appendix A for all subjects. The Fridericia formula for calculating QTc will be used (i.e., QTcF).

A shift table of the Investigator's assessment of ECG results at each visit compared with baseline values will be presented by treatment group using the following categories: normal; abnormal (not clinically significant); abnormal (clinically significant). The number and percentage of subjects in each cross-classification group of the shift table will be presented by treatment group. Subjects with a missing value at baseline or post baseline will not be included in the denominator for percentage calculation.

This document is confidential.

A by-subject listing will be provided, including each ECG parameter: ventricular heart rate (beats per minute [bpm]), PR interval [msec], RR interval [msec], QRS Duration [msec], QT interval [msec], QTcB interval [msec], QTcF interval [msec], and Investigator's interpretation. Potentially clinically significant QTcF values will be flagged in the listing.

The number and percentage of subjects with PCS and potentially clinically significant change (PCSC) values will be summarized by visit/timepoint and for any time post-baseline. Potentially clinically significant values will be identified for ECG parameters as outlined below.

Table 13.4.1 Potentially Clinically Significant Values for QT and QTcF

ECG Parameter	Units	Criteria for PCS Values (Observed values)		Criteria for PCS values (Change from Baseline values)	
		High	Low	Increase	Decrease
QT, QTcF	msec	>450 but <=480 >480 but <=500 >500	NA	>=30 to 60 >60	NA

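### Read with the SAP's earliest-value rule, the by-visit vital-sign and SpO2 abnormality table can count pre-dose readings and omit the scheduled post-dose ones

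*SAP*

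**What the plan says.** SAP section 7.4 uses nominal visits without derived windows. For repeated observations at a visit, with laboratory assessments as its example, it directs that "the earliest of the available non-missing values at a visit should be used in summary tables. Other observations will be considered as unscheduled visits". It adds that "the unscheduled post-baseline values generally will be excluded from summary tables but will be included in the listing". One exception is stated: "Unscheduled visits will be considered for analyses of worst Common Terminology Criteria for Adverse Events (CTCAE) laboratory grades".

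SAP section 11.5 plans two vital-sign outputs at different levels. Descriptive statistics "of actual values and changes from baseline will be presented for each visit and time point". For abnormalities, "Potentially clinically significant (PCS) vital sign abnormalities will be categorized based on Table 13.3.1 and summarized by treatment group and assessment visit". The second has no time point and no row for any time after baseline. The FEV1 abnormality counts in section 11.3 and the QT/QTcF counts in section 11.6 have both.

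SAP section 11.6 also plans a shift table of the Investigator's assessment, in which "ECG results at each visit compared with baseline values will be presented by treatment group". Percentages leave out subjects without a baseline or a post-baseline value. Under section 7.2.1, baseline is normally the last value before the first dose.

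Protocol Appendix A, Table 2 splits each dosing visit into scheduled time points, such as "30 minutes after first dose". Vital signs and SpO2 are taken before and after dosing at Visits 1, 2 and 3. ECGs are taken before dosing and 1 hour after the first dose, at Visit 1 only.

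**The concern.** Protocol section 1.3.2.2 names bronchial irritation and immune response as possible risks of nebulized phage, and gives them as the reason for close Day 1 monitoring that includes vital signs. The post-dose readings serve that purpose. SAP Table 13.3.1 sets the thresholds for SpO2, blood pressure and heart rate, and the PCS table is the planned count, by treatment group, of subjects beyond them.

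Section 7.4 picks one value per visit, the earliest. At a dosing visit that is the pre-dose reading unless it is missing. If the PCS table has one row per visit and follows that rule, an acute change after inhalation that has resolved by the next visit is not counted in it. The comparison between arms would then describe subjects just before they inhale.

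**Working it through.** The plan gives no figure to reproduce. The check applies the section 7.4 rule to the Table 2 schedule and counts the sets of readings kept and omitted.

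**Inputs.** Schedule: Protocol Appendix A, Table 2. Selection rule: SAP 7.4. Table level: SAP 11.5 and 11.6. Baseline: SAP 7.2.1. Thresholds: SAP Table 13.3.1.

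**Vital signs and SpO2**

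| Visit | Scheduled sets | Post-dose sets | Kept: earliest at visit | Post-dose omitted | Kept: earliest post-baseline | Post-dose omitted |
|---|---|---|---|---|---|---|
| 1 (Day 1) | pre-dose; 30 min after dose 1; 1 h after dose 2 | 2 | pre-dose | 2 | 30 min after dose 1 | 1 |
| 2 (Day 5) | pre-dose; 30 min after dose 1 | 1 | pre-dose | 1 | pre-dose | 1 |
| 3 (Day 10) | pre-dose; 30 min after dose 1 | 1 | pre-dose | 1 | pre-dose | 1 |
| Total | 3 + 2 + 2 = 7 | 2 + 1 + 1 = 4 | 3 | 4 of 4 | 3 | 3 of 4 |

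The last two columns give a milder reading: the Visit 1 pre-dose set is the baseline, so it is not eligible to represent a post-baseline visit.

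**Visit 1 change criteria.** On the literal reading the kept Visit 1 value is normally the baseline itself. Change = baseline − baseline = 0, so no change criterion (for example, an SpO2 decrease of at least 5) can be met in that row.

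**Illustration (assumed values).** SpO2 is 96% before dosing on Day 1, which is the baseline, and 89% at 30 minutes. Then 89 < 92 and 96 − 89 = 7 ≥ 5, so both SpO2 criteria are met. On the literal reading the Visit 1 row uses 96% and a change of 0, and the subject is not counted. The by-time-point descriptive summary still includes 89 and −7. The minimum printed in its 30-minute row is 89 or lower, and the minimum change is −7 or lower.

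**ECG shift table.** Visit 1 has two scheduled ECGs. The earliest is the pre-dose one, normally the baseline, so the literal reading compares baseline with itself and leaves out the 1-hour ECG. If the table is read as baseline against post-baseline, the only scheduled post-baseline ECG at Visit 1 is the 1-hour one, and it fills the row. Protocol Table 1 schedules no later ECG except at Day 38 or Early Termination.

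**After the proposed change.** All 4 post-dose vital-sign sets enter the PCS counts, against 0 (literal) or 1 (milder reading) now, and the 1-hour ECG enters the shift table under either reading.

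**The case against.** The strongest reply is that section 7.4 was never meant for planned time points. Its example is laboratory repeats, it says that values are generally excluded, and it is unnatural to call a scheduled 30-minute reading unscheduled. The by-time-point outputs in sections 11.5 and 11.6 would conflict with 7.4 if it reached that far. This is a fair reading and may well be the intended one. But 7.4 speaks of a visit and states no such limit. On the narrow reading, the SAP gives no rule at all for which of two or three scheduled readings represents a visit in the vital-sign PCS table. Either way the text has to be completed. Table shells, which are not in the documents, may already settle it.

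Two stronger inferences are tempting and are not supported:

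- A reader might infer that post-dose safety findings disappear from the report. They do not. Post-dose vital signs reach the descriptive summaries by visit and time point, with minimum and maximum, and the plots and listings. Post-dose QT/QTcF values reach the section 11.6 abnormality counts. Clinically significant abnormal findings are reported as adverse events (Protocol section 8.1), and FEV1 abnormalities are counted by time point and at any time post-baseline.
- A reader might infer that the ECG shift table definitely drops the post-dose ECG. The exclusion of subjects without a post-baseline value points to a baseline against post-baseline comparison, which would take the 1-hour ECG. The text is ambiguous and does not establish an omission.

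**Conclusion.** The point holds for one table. Taken literally, sections 7.4 and 11.5 fill the Visit 1 to 3 rows of the vital-sign and SpO2 PCS table with pre-dose readings. All 4 scheduled post-dose sets are left out, or 3 of 4 if the earliest post-baseline value is used. The loss is the categorical count by arm of threshold crossings after inhalation. For the ECG shift table the point is only that its Visit 1 row needs a stated source.

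This rests on four assumptions: the pre-dose reading is present (if it is missing, the earliest value is a post-dose one); the Visit 1 pre-dose value is the baseline; the Table 2 columns were read correctly from extracted text; and no unseen shell overrides the SAP wording. The Visit 2 and 3 pre-dose readings are on-treatment, so they remain informative about effects that persist between doses, though not about the acute response. Rows for Visits 4 to 7 are unaffected, since Table 2 sets no within-visit time points there.

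**What to change.** Three changes to the SAP, made before unblinding:

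1. In section 7.4, limit the earliest-value rule to repeats within the same scheduled time point, and state that planned pre-dose and post-dose readings are separate scheduled values.
2. In section 11.5, present vital-sign and SpO2 PCS counts by visit and time point and for any time post-baseline, in line with sections 11.3 and 11.6. State whether the any-time row includes unscheduled readings, because 7.4 generally keeps these out of tables.
3. In section 11.6, state that the Visit 1 row of the shift table uses the 1-hour post-dose ECG.

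The cost is a few sentences and two table shells. The readings are already scheduled, so no new data are needed.

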4.3.1 Criteria for Potential Interruption or Discontinuation of Study Drug in Individual Subjects

In the event that any of the following criteria are encountered, the Investigator will review the AE with the Medical Monitor as soon as feasible. The Investigator will hold the next administration pending that review. The Investigator and Medical Monitor in consultation with the Sponsor will decide whether to continue to hold study treatment pending additional information or to discontinue study treatment.

- \geq Grade 3 AE or laboratory abnormality per Common Terminology Criteria for AEs (CTCAE) version 5.0 considered attributable to AP-PA02 (confirmed by unblinding). If the event or laboratory test is not listed in the CTCAE, the event or laboratory test should be graded by applying the CTCAE guidelines detailed in [Section 8.1.3](#);

Note: Clinically significant laboratory abnormalities classified per above should be confirmed with a repeat test within 24 hours.

- Any serious AE (SAE) considered attributable to AP-PA02 (confirmed by unblinding); or
- Acute bronchospasm, defined as a decrease in absolute FEV₁ of \geq 15% accompanied by symptoms requiring medical intervention, occurring from the Baseline value up to 4 hours following study drug administration and persisting following administration of a short-acting bronchodilator.

Any subject who prematurely discontinues from study drug, will have documented the reason and date of discontinuation in the electronic case report form (eCRF) and the subject should be encouraged to continue to complete all safety and key efficacy assessments at subsequent study visits. For subjects who do not agree to participate in subsequent study visits, study staff should make every effort to complete the full panel of assessments scheduled for the Early Termination (ET) Visit.

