Biomarkers		X	X	X	X	X	X	X	X	X
Expectorated sputum sample (if able to provide)		*	*	*	*	*	*	*	*	*
Sputum culture ^k		X		X	X	X	X	X	X	X
Sputum phage titer		X	X	X	X	X	X	X	X	X
Blood phage titer ^m		X	X	X	X	X	X	X	X	X
Urine phage titer ⁿ		X				X				X
Randomization		X								
Distribute sputum and urine collection containers			X							
Daily symptom diary		Dispense	Review	Review	Review	Review	Review	Review	Collect	Collect

Table 1. Schedule of Assessments (Continued)

Visit	Screening Period	Baseline	Treatment Period			Safety Follow-Up Period				Early Termination
	Screening	Baseline	1	2	3	4	5	6	7/EOS	ET
Day	-35 to -2	-7 to -1	1	5	10	11	17	24	38	U
Visit Window							(±3d)	(±3d)	(±3d)	
Dispense study drug for home administration ^o			X	X	X					
Study drug administration training			X							
Study drug administration ^p			X	X	X					
Antibiotic administration ^q		X	X	X	X	X	X	X		
QOL-B Questionnaire		X				X		X		
LCQ		X				X		X		
Saint George's Respiratory Questionnaire		X							X	
Anti-phage antibody titer		X						X	X	X
AEs/SAEs ^r	X	X	X	X	X	X	X	X	X	X

Note: If a subject withdraws prematurely from the study, study staff should make every effort to complete the full panel of assessments scheduled for the ET Visit. See the Timing of Sample Collection and Procedures for the Treatment Period table for sample collection and procedure timing during the Treatment Period. The Treatment Period may be up to 28 days for the optional cohorts.

- Signed informed consent must be obtained before any study-related procedures are performed.
- Any updates since the Baseline Visit will be assessed.

- c. HIV antibody, HBsAg, and HCV antibody testing will be performed at Screening, only if status is unknown. Height will be collected at the Screening Visit only and will be used to calculate body mass index and percent predicted spirometry values by GLI standards.
- d. A full physical examination will be performed at the Screening Visit, Baseline Visit, and the EOS Visit. A symptom-directed physical examination will be performed at the other visits.
- e. Vital signs include blood pressure, heart rate, respiratory rate, and body temperature.
- f. FEV₁, FVC, and FEF₂₅₋₇₅ will be collected. Actual liter values will be recorded. Study eligibility will be based on percent predicted value using GLI standards, which requires race and ethnicity information as part of the GLI calculation. Spirometry will be collected prior to sputum induction on non-Treatment Period Visits.

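### SAP 7.4 has no rule for Early Termination values: a culture taken then inside the Visit 5 window misses the primary Day 17 comparison, and some safety values may miss the any-time post-baseline counts

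*SAP*

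**What the plan says.** **Protocol.** Table 1 in Appendix A has a separate ET column. Its entry in the Day row is U, explained below the table as "U = Unscheduled". The column is marked for induced-sputum culture, spirometry, vital signs and SpO2, 12-lead ECG and laboratory tests. For a subject who withdraws early, the table note says "study staff should make every effort to complete the full panel of assessments scheduled for the ET Visit". Section 4.3.1 covers subjects who stop study drug: "the subject should be encouraged to continue to complete all safety and key efficacy assessments at subsequent study visits". The ET visit is for those who do not agree to that. Visit 5 is Day 17 with a window of 3 days either side.

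**SAP.** Section 7.4 states: "There will be no derivation for visit windows in terms of summary assessments. Nominal visits will be used for by-visit tables". Where a visit has repeated values, the earliest non-missing one is used, and "Other observations will be considered as unscheduled visits". It then sets the rule for tables: "For the purpose of tabulations, the unscheduled post-baseline values generally will be excluded from summary tables but will be included in the listing". Worst CTCAE laboratory grade is the only exception named there. Section 7.3 does not impute missing endpoint data. Section 9.1 defines the primary analysis, by cohort, as the change from baseline in log10 density in induced sputum at Visit 5/Day 17, reported as a 95% confidence interval without a p-value.

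Potentially clinically significant (PCS) values are counted by visit and at any time post-baseline for FEV1 (Section 11.3) and QT/QTcF (Section 11.6). For vital signs and SpO2 they are counted by assessment visit only (Section 11.5). The SAP text does not name the ET visit.

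**The concern.** Sites are asked to work hard for the ET panel, but the SAP does not say where its values go. Two outputs are exposed.

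- **Primary comparison.** A subject who leaves the study on, say, Day 16 and gives an induced sputum at the ET visit has a culture within the tolerance already allowed for Visit 5. With no assignment by study day and no imputation, that subject counts as having no Visit 5 value.
- **Any-time safety counts.** These exist to catch an abnormal value whenever it occurs. If unscheduled values are kept out of them, an abnormal FEV1 or QTcF found at an unplanned check, or at ET, is not counted.

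The arms are small, so one subject moves a percentage or an interval noticeably. A rule chosen after treatment codes are known would be open to question.

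**Working it through.** The plan gives no power, SD, effect size or dropout rate, so there is no figure of its own to reproduce. The check is a reading of the rules, followed by an illustration of size.

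**1. Windows.** With 3 days either side (Protocol Table 1):
- Visit 5: 17 ± 3 = Days 14 to 20
- Visit 6: 24 ± 3 = Days 21 to 27
- Visit 7: 38 ± 3 = Days 35 to 41

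The windows do not overlap, so assignment by study day would be unambiguous.

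**2. An ET culture on Days 14 to 20, under each reading of ET.**
- *ET is unscheduled.* SAP 7.4 generally keeps the value out of summary tables, so it is not a Visit 5 value.
- *ET is a nominal visit with its own row.* The value is shown under ET. As nothing is moved by study day, it is again not a Visit 5 value.

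Section 9.1 takes the endpoint at Visit 5, and Section 7.3 leaves a missing endpoint missing. Both readings lead to the same loss, so the primary point does not depend on how the label is read.

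**3. Safety values.**
- *FEV1 and QT/QTcF.* An any-time count is planned, but neither section says that it includes unscheduled or ET values. The general rule in 7.4 excludes unscheduled values, and the laboratory exception suggests that inclusion has to be stated.
- *ECG timing.* After Day 1, Table 1 schedules an ECG only at Visit 7 and ET. For a subject who leaves in between, ET is the only later planned ECG.
- *Vital signs and SpO2.* The PCS table has no any-time row. An unscheduled abnormal value has no place in it, nor does an ET value unless ET has its own row.

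**4. Size of one lost value.** At 2:1 allocation of 24, the arms are 16 and 8.
- Primary: 1/16 = 6.25% of the active arm, 1/8 = 12.5% of placebo, 1/24 = 4.2% of the cohort.
- Safety: one subject whose only PCS value is uncounted shifts the any-time rate by 6.25 percentage points in an arm of 16, or 12.5 in an arm of 8.

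**5. Effect on the primary interval.** Half-width in SD units = t(0.975, n1+n2−2) × √(1/n1 + 1/n2). The losses are assumed.

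| Active : placebo | Half-width (SD) | Change from 16:8 |
|---|---|---|
| 16:8 | 0.898 | none |
| 15:8 | 0.910 | +1.4% |
| 16:7 | 0.942 | +4.9% |
| 15:7 | 0.955 | +6.3% |
| 14:6 | 1.025 | +14.2% |

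SAP Section 6 removes AP-PA02 subjects enrolled before the first DSMB meeting from most summaries. The analysed active arm may therefore be below 16, and each value would then weigh more.

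**The case against.** The strongest objection is that the SAP never calls ET unscheduled. The U stands in the Day row of a named visit and may mean only that the day cannot be fixed in advance. The protocol itself speaks of "study staff should make every effort to complete the full panel of assessments scheduled for the Early Termination (ET) Visit", which treats the panel as planned. In SAP 7.4 the word is applied to surplus repeat values at one visit, and "Nominal visits will be used for by-visit tables" fits an ET row equally well. This stands: placing ET under the exclusion is an inference. It weakens the safety half for ET values, but not for other unscheduled values, and it leaves the primary half untouched.

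A reader might also infer that the last results of early leavers are left out altogether and that tolerability losses are hidden. The documents do not support that:
- All safety data are listed.
- The spirometry plots expressly include unscheduled results, and by-subject plots are planned for culture density, laboratory values and vital signs.
- Worst laboratory grades include unscheduled visits.
- Adverse events leading to withdrawal of study drug and reasons for discontinuation are tabulated, and Protocol 8.1 has abnormal findings that require intervention or action with study drug reported as adverse events.

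Finally, the group is narrow. Subjects who only stop drug are encouraged to keep their scheduled visits. The primary loss needs a subject who leaves on Days 14 to 20 without a Visit 5 and whose culture is recorded under ET. This also stands, and it limits the size of the point rather than removing it.

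**Conclusion.** The point holds in limited form. Under either reading of ET, an induced culture taken at that visit on Days 14 to 20 does not reach the primary Day 17 comparison. Under the general rule in SAP 7.4, unscheduled FEV1 and QT/QTcF values, and ET values if treated as unscheduled, may be left out of the any-time PCS counts. The vital-sign/SpO2 PCS table has no any-time count at all.

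The number of subjects affected is unknown and probably small. If one placebo culture were lost from a full 16:8 cohort, the interval would widen by 4.9%; one active and one placebo lost would widen it by 6.3%. These figures assume complete arms otherwise and a common SD. They illustrate the stakes and do not estimate the loss. The reading that results are discarded or tolerability concealed goes too far. This is a cheap improvement, not a threat to the trial's validity.

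**What to change.** Before unblinding, add two rules to SAP 7.4:

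1. An ET value is assigned by actual study day to Visit 5, 6 or 7 when it falls within that visit's 3-day window either side and the visit has no value of its own. This applies to the primary Visit 5 culture, which must still be induced sputum and pass the specimen exclusions in Section 9.1.
2. ET and unscheduled post-baseline values count in the any-time post-baseline PCS summaries for FEV1 and QT/QTcF, and the same any-time row is added for vital signs and SpO2. This matches what is already done for worst laboratory grade.

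How ET values outside every window are displayed is a matter of preference.

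The cost is a short SAP edit and a small visit-mapping step in the analysis datasets. A few ET values up to 3 days from the nominal day would enter a visit, the same tolerance already allowed for attended visits.
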